## **6 DATA HANDLING**

### **6.1 Visit window**

The below time windows for visit/timepoints will be used for analyses:

Analysis Visit	Scheduled Day	Visit Window
Baseline	Up to Day 1	≤ Day 1 Last non-missing measurement taken prior to first Investigational Medicinal Product (IMP) administration in study CLIN-60120-452
Month 6	182	Day 2-274
Month 12	365	Day 275-456
Month 18	547	Day 457-639
Month 24	730	Day 640-821
Month 30	912	Day 822-1003
Month 36	1095	≥ Day 1004

For post-baseline visit windows, the following applies when there are multiple assessments in a particular visit window, the closest to the scheduled day is chosen (if two assessments have the same distance, then the later one will be chosen).

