1.3 Schedule of Activities

The schedule of activities (SoA) planned in this study are presented in [Table 1](#).

Table 1 Schedule of Activities

Assessment/Procedure	Inclusion Visit[a] Day 1			Follow-Up Visits Every 6 months (± 1 month)[b]/ EOS/EW Visit[c]	
	Procedures already performed at the parent EOS Visit that will be transferred from parent study database	Procedures already performed at the parent EOS Visit to be entered in CLIN-60120-452 eCRF by the study site	Procedures to be performed at the CLIN-60120-452 Inclusion Visit	In-clinic Visit	Remote visit
Informed consent[d]			X		
Inclusion/exclusion criteria			X		
Study intervention administration/accountability[e]			X	X	X
Baseline demographics			X		
Physical examination			X		
Participant interview[f]			X		
Pregnancy testing and childbearing potential [g]		X[a]*		X	X
Linear height and body weight [h]		X[a]*		X	X
Vital signs [i]		X[a]*		X	X
Spinal health assessment [j]		X [a]**		X	
Lung function assessments [k]			X	X	
Flare-up assessment [l]			X	X	X [m]
Additional Extra bone growth assessment (without associated flare-up)			X	X	X
CAJIS [n]	X*			X	X
C-SSRS [n] [o]			X	X	X
FOP-PFQ assessment[p] [q]	X*		X [q]***	X	X
PROMIS Global Health Scale [p][q]	X*		X [q]***	X	X
FOP assistive devices assessment [p]			X	X	X
Healthcare Utilization [p]			X	X	X
Biochemistry (amylase, lipase, AST, ALT) and triglycerides	X*				
Disease and flare-up history	X				
Prior medications	X				
Concomitant medications		X		X	X
Concomitant procedures [r]		X		X	X
AEs [s]		X		X	X

AE=adverse event; ALT=alanine aminotransferase; AST=aspartate aminotransferase; CAJIS=Cumulative Analogue Joint Involvement Scale for FOP; COVID-19=coronavirus disease 2019; C-SSRS=Columbia-Suicide Severity Rating Scale; DLCO=diffusion capacity of the lung for carbon monoxide; eCRF=electronic case report form; EOS=End of Study; EW=Early Withdrawal; FEV₁=forced expiratory volume in one second; FVC=forced vital capacity; FOP=fibrodysplasia ossificans progressiva; FOP-PFQ=FOP Physical Function Questionnaire; PROMIS=Patient Reported Outcomes Measurement Information System.

a. The Inclusion Visit should be in-clinic and corresponds ideally to the EOS Visit of the parent study (Study PVO-1A-301 or PVO-1A-202/PVO-1A-204). A maximum of one month is allowed between the two visits. For any assessments

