from the parent EOS Visit performed outside this allowed time window, assessments will need to be performed again at the Study CLIN-60120-452 Inclusion Visit (flagged with *). However, to enable continued access to the Investigational Product and rollover of participants with impaired mobility [in the case(s) when per investigator's judgement this is considered as beneficial for the participant's medical conditions], the parent EOS Visit and consenting for CLIN-60120-452 and CLIN-60120-452 Inclusion Visit can be conducted remotely. In such case(s) both parts of remote consenting used by the site – i.e. Informing/Consenting discussion and ICF signature should be agreed with the IRB/EC, and the investigator's judgement should be sufficiently documented in the patient source notes.

For the spinal health assessment, a time window of 3 months post parent visit is allowed (flagged with **).

- b. Follow-up Visits will be either in-clinic or performed remotely (e.g. at the participant's home by qualified SP in-home services, and/or via video-conference or telephone contact from clinical site personnel).
- c. The EOS/EW Visit will be ideally an in-clinic visit (or remotely when permitted by the IRB/IEC) and will occur at the time of last study intervention intake. The EOS Visit must take place before the participant transitions to commercial treatment.
- d. For participants <18 years, assent and legal guardian's consent will also be required.
- e. Palovarotene status (treated or not treated) and regimen (chronic or flare-up treatment) at the time of transition to Study CLIN-60120-452 will be collected at the Inclusion Visit. Participants will be supplied with chronic treatment as well as the appropriate dose of palovarotene to initiate flare-up treatment when a flare-up or traumatic event is confirmed by the investigator. Participants will be instructed to report potential flare-up symptoms to study site personnel, only one symptom is required to define a flare-up (see Section 6.1). In the presence of persistent flare-up symptoms, treatment may be extended in 4-week intervals until the flare-up symptoms resolve. If the participant experiences an intercurrent flare-up, or substantial high-risk traumatic event likely to lead to a flare-up, at any time during the flare-up treatment, the 12-week flare-up treatment should be restarted.

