8.2.2 C-SSRS and Suicidal Ideation and Behaviour Risk Monitoring

Suicidal ideation and behaviour will be collected using the C-SSRS ('Baseline' version) at the Inclusion Visit for screening purposes. At Follow-up visits, the C-SSRS 'Since Last Visit' version will be used.

The adult form (designed for participants ≥ 12 years of age) will be used for all participants. Any participant reporting type 4 or 5 suicidal ideation or any suicidal behaviour within the past month prior to the Inclusion Visit, will not be eligible to participate in the study.

Although there was no treatment-related increase in suicidal ideation, suicidal behaviour or psychiatric disorders overall relative to untreated participants with FOP in clinical trials, depression, depression aggravated, anxiety, mood alterations and suicidal thoughts and behaviours have been reported in patients treated with systemic retinoids. In addition, there is a relatively high background prevalence (24%) of depression in untreated patients with FOP.

Therefore, participants being treated with palovarotene should be monitored appropriately and observed closely for suicidal ideation and behaviour or any other unusual changes in behaviour, especially at the beginning and end of the course of intervention, or at the time of dose changes, either increases or decreases. Participants who experience signs of suicidal ideation or behaviour should undergo a risk assessment. All factors contributing to suicidal ideation and behaviour should be evaluated and consideration should be given to discontinuation of the study intervention.

When informed consent or assent has been given, families and caregivers of participants being treated with palovarotene should be alerted about the need to monitor participants for the emergence of unusual changes in behaviour, as well as the emergence of suicidal ideation and behaviour and to report such symptoms immediately to the study investigator. Suicidal ideation and behaviour will be captured as an AE/SAE.

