## 2.2 Overall Study Design and Investigational Plan

Study CLIN-60120-452 is a multicentre, noncomparative rollover study with the aim of continuing to provide palovarotene to participants with FOP who have completed one of the

parent studies (Study PVO-1A-301 or PVO 1A 202/PVO 1A 204) and, in the investigator's judgement, may benefit from palovarotene therapy. Participants who have completed the parent study are defined as those who have completed the parent End of Study (EOS) or End of Treatment Visit.

[figure not shown]
The study is designed primarily to further evaluate the safety of palovarotene and secondly, to collect efficacy data in male and female participants aged  $\geq 14$  years (qualifying as skeletally mature or, based on investigator's assessment, have reached final adult height) with FOP treated with palovarotene.

Participants are eligible for the study whether they are receiving chronic or flare-up treatment in the parent study at the time of transition. Participants who previously interrupted/stopped palovarotene treatment and are currently under parent study follow-up due to the premature physeal closure (PPC) related partial clinical hold in participants  $<14$  years, are eligible for the study if they are  $\geq 14$  years of age and skeletally mature/have reached final adult height based on investigator's assessment. There must be a current parent study signed informed consent (ICF) form for the participant to be eligible for Study CLIN-60120-452.

A maximum of 87 participants from studies PVO-1A-301, PVO-1A-202/PVO-1A-204 are eligible to be enrolled and will receive palovarotene once daily at the dose received during their participation in the parent study at the time of transition to Study CLIN-60120-452 or prior to interrupting/stopping palovarotene treatment.

The study will consist of an Inclusion Visit (Day 1) (which ideally corresponds to the parent EOS Visit), a continuous dosing treatment period (including a Follow-up Visit every six months), and an EOS/Early Withdrawal (EW) Visit. The maximum duration is three years from enrolment to last study visit (November 2021 to November 2024). The study schema is below:

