#### *5.1.1.3 Presentation of Visits / Timepoints*

Summaries by visit will be presented using the derived window visits (See Section 6.1). Visits in the TFLs will be presented as follows and in the following order:

Visit Name
Baseline
Month 6
Month 12
Month 18
Month 24
Month 30
Month 36

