### 5.8.4 C-SSRS

A summary of the number and percentage of participants with any type of suicidal ideation or behaviour (yes/no) will be presented at each visit. The number of questionnaires completed and the CSSRS suicidal ideation score will be also presented at each visit. Suicidal ideation includes the categories:

- Wish to be dead
- Non-specific active suicidal thoughts
- Active suicidal ideation with any methods (not plan) without intent to act
- Active suicidal ideation with some intent to act, without specific plan
- Active suicidal ideation with specific plan and intent

Whereas suicidal behaviour includes:

- Preparatory acts or behaviour
- Aborted attempt
- Interrupted attempt
- Non-fatal suicide attempt
- Completed suicide

In addition, a shift table from the inclusion visit to each post-inclusion visit of no suicidal ideation or behaviour, any suicidal ideation and any suicidal behaviour will be presented. Participants with both suicidal ideation and suicidal behaviour are included in the suicidal behaviour category.

Similarly, a shift table of maximum suicidal ideation assessments from the inclusion visit to each post-inclusion visit will be presented. Maximum refers to the maximum C-SSRS suicidal ideation score during treatment (0 = least severe, 5 = most severe) where 0=No Suicidal Ideation, 1=Wish to be Dead, 2=Non-specific Active Suicidal Thoughts, 3=Active Suicidal Ideation with Any Methods (Not Plan) without Intent to Act, 4=Active Suicidal Ideation with Some Intent to Act, without Specific Plan, and 5=Active Suicidal Ideation with Specific Plan and Intent.

All participants who report any type of suicidal ideations in the C-SSRS or any suicidal behaviour during the study will be presented in listings.

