### **6.2 Unscheduled Visits, Retest, Withdrawal Visit**

All listings will include retests and unscheduled visits, while for the description by visit in the tables, only the scheduled visits according to the protocol will be described.

Unscheduled visit and retest measurements will be used to provide a measurement for a baseline data or endpoint value (e.g. worst value), if appropriate according to their definition. These measurements will also be used to determine PCS vital signs values.

If a value requires a retest (for vital signs) or there is an unscheduled visit the closest non-missing reliable value to the scheduled visit will be used in the summary tables.

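### The SAP has no End of Study/Early Withdrawal row and keeps one record per window, so a final assessment made soon after a follow-up visit can drop out of the scale, vital-sign and main C-SSRS by-visit tables

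*SAP*

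**What the plan says.** Protocol Table 1 (section 1.3) puts the EOS/EW visit in the same columns as the "Follow-Up Visits Every 6 months" (± 1 month). Footnote c adds that it "will occur at the time of last study intervention intake". For an individual, that day is set by reimbursement, another access programme, the November 2024 end date or withdrawal (Protocol 4.4 and 7). Sections 8.1.1 to 8.1.6, 8.2.4 and 8.2.5 ask for FOP-PFQ, PROMIS, CAJIS, assistive devices, lung function, height/weight and vital signs at EOS/EW, and Table 1 asks for the C-SSRS.

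SAP 5.1.1.3: "Summaries by visit will be presented using the derived window visits". The rows are Baseline and Months 6, 12, 18, 24, 30 and 36. SAP 6.1 gives one window per row and says that "when there are multiple assessments in a particular visit window, the closest to the scheduled day is chosen", the later one winning a tie. SAP 6.2 names the withdrawal visit in its heading. Its text says that in tables "only the scheduled visits according to the protocol will be described", and gives no rule for the withdrawal visit.

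For the C-SSRS, SAP 5.8.4 says that the number of participants with "any type of suicidal ideation or behaviour (yes/no) will be presented at each visit", and adds shift tables. Protocol 8.2.2 asks for close observation "especially at the beginning and end of the course of intervention".

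**The concern.** The protocol collects a full set of assessments at the end of treatment, but the SAP has no row for them. They enter a by-visit table only if they are alone in a month window or nearer to its nominal day than the follow-up visit. Take a visit on Day 547 and EOS on Day 620. Both lie in the Month 18 window (Day 457–639), at distances of 0 and 73 days, so the Day 620 values are left out.

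For a scale such as CAJIS this removes the last on-treatment value. For the C-SSRS it does more. Post-baseline visits use the version that asks about the time since the last visit (Table 1 footnote o names it for follow-up visits; I take it to apply at EOS/EW, which shares the column). Two forms in one window then cover different periods and cannot stand in for each other. An event reported only at EOS/EW can be missing from the yes/no incidence and from the ideation/behaviour shift table, in a period that the protocol singles out for observation.

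A related effect concerns labels. The Month 6 window opens on Day 2, so an early-withdrawal assessment on Day 20 would be tabulated as Month 6.

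**Working it through.** The documents give no figure for the share displaced, so there is none to reproduce.

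**Inputs.** Nominal days 182, 365, 547, 730, 912 and 1095, with windows ending on Days 274, 456, 639, 821 and 1003 and the last one open (SAP 6.1). Maximum follow-up is three years, about Day 1095 (SAP 2.2). Visit tolerance is ± 1 month (Table 1), taken as ± 30 days. The distribution of EOS/EW days is **not given**; I assume it is uniform and vary the range.

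**Exact count, follow-up visits on the nominal days.** Any EOS/EW day after the nominal day and inside the same window loses to the visit. The days concerned are:

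- Month 6: 274 − 182 = 92
- Month 12: 456 − 365 = 91
- Month 18: 639 − 547 = 92
- Month 24: 821 − 730 = 91
- Month 30: 1003 − 912 = 91
- Month 36: none up to Day 1095

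Total: 457 days. With EOS/EW uniform over Day 183–1095 (913 days), 457/913 = 50.1%. Over Day 2–1095 (1094 days), 457/1094 = 41.8%.

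**EOS/EW takes the place of a visit due shortly before it.** If it replaces a visit due within the previous 30 days, each of the five windows loses 30 days: (457 − 150)/913 = 33.6% and 307/1094 = 28.1%. For 60 days: (457 − 300)/913 = 17.2% and 157/1094 = 14.4%.

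**Visits off the nominal day** (simulation, 20,000 per scenario), set beside the exact results:

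| Follow-up visits | EOS/EW Day 2–1095 | EOS/EW Day 183–1095 |
|---|---|---|
| On nominal days | 41.8% | 50.1% |
| Uniform within ± 30 days of nominal | 34.2% | 41.8% |
| About 182 days after the previous visit, ± 30 days | 30.8% | 37.2% |
| Nominal; EOS/EW replaces a visit due in the last 30 days | 28.1% | 33.6% |
| Nominal; the same with 60 days | 14.4% | 17.2% |

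The lower end is not a floor. If every visit runs 0 to 30 days late and the delays accumulate, the shares are 21.4% and 25.8%, and 2.3% and 2.7% if a 60-day replacement is added.

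**Extremes.** 0% if every EOS/EW visit takes the place of a due visit or comes before the Month 6 visit. 100% if all participants finish in Day 913–1003 after a Month 30 visit on Day 912.

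**In participants.** 14.4% and 50.1% of 87 are 12.5 and 43.6, so about 13 to 44. The figure of 87 is the maximum eligible, not the number enrolled.

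**Which outputs are thinned.** The closest-record rule applies where one value per window is tabulated: CAJIS, FOP-PFQ, PROMIS, lung function, assistive devices, height/weight, vital signs, and the C-SSRS yes/no and category-shift tables. For lung function it applies only when both visits were in clinic, since Table 1 does not schedule it remotely. These outputs are not thinned:

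- Flare-up and extra-bone-growth counts, which total all distinct records in a window by start date (SAP 5.7.3.7, 5.7.3.8)
- Annualised healthcare use and monthly flare-up rates, which use the whole study (SAP 5.7.3.5, 5.7.3.7)
- TEAE tables (SAP 5.7.2.2)
- New-onset potentially clinically significant vital signs, which are not limited to one record per window (SAP 5.8.6, 6.2)

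**The case against.** The scale and lung-function endpoints are defined at each follow-up visit, and the Month 6 to 36 rows deliver that. The study is descriptive, the primary endpoint is TEAEs, and everything is listed. A displaced EOS/EW value is never far from a retained one: at most 92 days if the visit was on time, or 122 days if it was 30 days early. An EOS/EW assessment alone in its window is kept under the month label. All of this stands, and for the scales it makes the loss modest. It does not answer the C-SSRS point, because a form covering an earlier period cannot replace one covering a later period.

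A reader might infer four stronger things that the documents do not support:

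- **That every by-visit table loses the final data.** Flare-up and bone-growth counts do not.
- **That a suicidal event reported at EOS/EW would appear only in a listing.** Protocol 8.2.2 has suicidal ideation and behaviour captured as an AE/SAE, so a new or worsened event should reach the TEAE tables. SAP 5.8.4 also defines one shift table by the maximum ideation score during treatment. That table covers ideation and not behaviour, and its layout by visit is unclear.
- **That SAP 6.2 shuts out the EOS/EW visit altogether as unscheduled.** Table 1 schedules it.
- **That participants who withdraw because they are doing badly are lost selectively.** Nothing in the documents shows this.

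**Conclusion.** The point holds for the outputs that use one record per window. The SAP states a rule that can discard the end-of-treatment assessment in favour of an earlier one, and it has no row or withdrawal-visit rule to prevent this. The primary endpoint is untouched.

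The size depends on EOS timing, which is unknown. It is about 14–50% if EOS dates are uniform over follow-up, and lower still if visits run consistently late. The narrower 42–50% needs three further assumptions: everyone stays past Month 6, a separate follow-up visit always precedes EOS, and visits fall within ± 30 days of the nominal day. It should not be quoted without them.

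The practical consequence is greatest for the C-SSRS incidence and category-shift tables. For the scales, the loss is a final value within about three to four months of a retained one.

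**What to change.** - In SAP 5.1.1.3 and 6.1, add an End of Study/Early Withdrawal row to the secondary and safety by-visit tables that use one record per window. Fill it from each participant's EOS/EW visit, with change from Inclusion and the median study day. Keep the Month 6 to 36 rows.
- In SAP 6.2, state how the EOS/EW visit is handled.
- In SAP 5.8.4, use the worst C-SSRS result among all assessments in a window, and add one row for any time post-Inclusion.

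The data are already collected, so the cost is SAP wording and an extra row per table. The drawback is that the new row mixes follow-up durations, which is why it should show the median study day. With the row in place, no EOS/EW assessment that was made would be left out of these tables.

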### **6.2 Unscheduled Visits, Retest, Withdrawal Visit**

All listings will include retests and unscheduled visits, while for the description by visit in the tables, only the scheduled visits according to the protocol will be described.

Unscheduled visit and retest measurements will be used to provide a measurement for a baseline data or endpoint value (e.g. worst value), if appropriate according to their definition. These measurements will also be used to determine PCS vital signs values.

If a value requires a retest (for vital signs) or there is an unscheduled visit the closest non-missing reliable value to the scheduled visit will be used in the summary tables.

## **7 DERIVED DATA**

### **7.1 PROMIS T-Score Conversions**

The following conversion tables allow a user to convert Global Physical Health, Global Mental Health, and Total scores into T-scores. T-score distributions are standardized such that a 50 represents the average (mean) for the US general population, and the standard deviation around

that mean is 10 points. A high score always represents more of the concept being measured. Thus, a participant who has a T-score of 60 is one standard deviation better (healthier) than the general population.

Global Physical Health			Global Mental Health		
Raw Score	T-Score	Standard Error	Raw Score	T-Score	Standard Error
4	16.2	4.8	4	21.2	4.6
5	19.9	4.7	5	25.1	4.1
6	23.5	4.5	6	28.4	3.9
7	26.7	4.3	7	31.3	3.7
8	29.6	4.2	8	33.8	3.7
9	32.4	4.2	9	36.3	3.7
10	34.9	4.1	10	38.8	3.6
11	37.4	4.1	11	41.1	3.6
12	39.8	4.1	12	43.5	3.6
13	42.3	4.2	13	45.8	3.6
14	44.9	4.3	14	48.3	3.7
15	47.7	4.4	15	50.8	3.7
16	50.8	4.6	16	53.3	3.7
17	54.1	4.7	17	56	3.8
18	57.7	4.9	18	59	3.9
19	61.9	5.2	19	62.5	4.2
20	67.7	5.9	20	67.6	5.3

PROMIS=Patient Reported Outcomes Measurement Information System.

## 7.2 Linear Height Z-scores

The linear height z-scores will be calculated using the reference population from the Centers for Disease Control and Prevention (CDC):

<https://www.cdc.gov/nccdphp/dnpao/growthcharts/resources/sas.htm>.

The Z-scores will be derived by following the below steps:

- (1) Download the reference file and SAS code from the above link
- (2) Create a temporary dataset that contains the height (cm), sex (1 for males and 2 for females) and age (months) of each participant.
- (3) The SAS code should be executed to generate the Z-score based upon the reference population.

## 9 APPENDICES

### A1. SAS code

No predefined SAS code is required.

### A2. List of PCSA criteria

#### PCSA for Vital Signs parameters:

	PCS Low	PCS High
Systolic blood pressure	<86 mmHg or a decrease of $\geq 25$ mmHg from baseline	>180 mmHg or an increase of $\geq 25$ mmHg from baseline
Diastolic blood pressure	<48 mmHg or a decrease of $\geq 20$ mmHg from baseline	>110 mmHg or an increase of $\geq 20$ mmHg from baseline
Heart rate	<45 bpm or a decrease of $\geq 20$ bpm from baseline	(1) >105 bpm AND an increase of $\geq 20$ bpm from baseline (2) >125 bpm

mmHg = millimeters of mercury, bpm = beats per minute.

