8.2.5 Vital Signs

Respiratory rate, blood pressure and heart rate will be collected at the Inclusion Visit, the Follow-up Visits and the EOS/EW Visit.

- Blood pressure and pulse measurements will be assessed by manual techniques. An automated device should not be used due to the risk of over-inflation and potential tissue injury in participants with FOP. To minimise the potential for a flare-up at the cuff site when measuring blood pressure, the cuff should be pumped slowly to a maximum of 140 mm Hg. Blood pressure should not be measured on an arm with a flare-up.
- Blood pressure and pulse measurements should be preceded by at least 5 minutes of rest for the participant in a quiet setting without distractions (e.g. television, cell phones).
- Vital signs will be measured after 5 minutes rest and will include respiratory rate, systolic and diastolic blood pressure and pulse.

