9.2 Sample Size Determination

No formal sample size calculations have been performed as the sample size is dependent on the number of participants in the parent studies who are eligible. A maximum of 87 participants from studies PVO-1A-301, PVO-1A-202/PVO-1A-204 are eligible to be enrolled.

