### **5.8.6 *Vital Signs***

Vital signs include systolic blood pressure [mmHg], diastolic blood pressure [mmHg], heart rate [beats/min] and respiratory rate [breathes/min].

A summary of all vital sign variables (vital sign raw values and changes from inclusion visit) will be calculated for each visit for the FAS/SAS with descriptive statistics.

Potentially clinically significant (PCS) values are predefined criteria/thresholds presented in Appendix A2.

New-onset PCS values are defined as values that were not PCS at baseline and were PCS post-baseline. New-onset PCS values post-baseline will be summarised with counts and percentages. In addition a shift table from inclusion visit to each post-inclusion visit will be presented by abnormality (low, normal, high) as defined by the below criteria:

In addition a shift table from inclusion visit to each post-inclusion visit will be presented by abnormality (low, normal, high) as defined by the below criteria:

	Low	Normal	High
Systolic blood pressure	<86 mmHg	86 – 180 mmHg	>180 mmHg

	Low	Normal	High
Diastolic blood pressure	<48 mmHg	48 – 110 mmHg	>110 mmHg
Heart rate	<45 bpm	45 – 125 bpm	>125 bpm
mmHg = millimeters of mercury, bpm = beats per minute.			

A listing of all vital sign data and PCS values will be presented.

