#### **A4. Programming Convention for Outputs**

All text fields must be left justified and numeric or numeric with some text specification (e.g.: not done, unknown, <4.5, ...) must be decimal justified.

The mean, median, lower quartile, upper quartile, SD and standard errors (SE) of the mean/median 95% confidence interval values will be reported to one decimal place greater than the raw data recorded in the database.

The minimum and maximum values will be reported with the same number of decimal places as the raw data recorded in the database.

In general, the maximum number of decimal places reported should be four for any summary statistic.

Percentages will be presented to one decimal place. Percentages will not be presented for zero counts. Percentage will be calculated using n as denominator. The denominator n will be specified in a footnote for clarification if necessary. If sample sizes are small, the data displays will show the percentages, but in the CSR only frequency counts should be described.

All values below or above a limit of detection (e.g. <0.1 or >100) will be listed as such.

Dates will be presented in the format [ddmmmyyyy] and times in the format [hh:mm].

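### Under the protocol's 140 mmHg cuff limit, the SAP's absolute systolic High criterion (above 180 mmHg) cannot be observed, and capped readings have no classification rule

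*SAP*

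**What the plan says.** Protocol 8.2.5: "Blood pressure and pulse measurements will be assessed by manual techniques". Automated devices are not to be used, because over-inflation could injure tissue in FOP. To limit the risk of a flare-up at the cuff site, "the cuff should be pumped slowly to a maximum of 140 mm Hg".

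The SAP has two separate rules for high systolic pressure:

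- **Shift table (5.8.6).** Results are cross-tabulated from the inclusion visit to each later visit "by abnormality (low, normal, high) as defined by the below criteria". The systolic bands are absolute: Low below 86, Normal 86 to 180, High above 180 mmHg.
- **PCS High (Appendix A2).** The criterion is ">180 mmHg or an increase of" at least 25 mmHg from baseline. It feeds the new-onset table in 5.8.6: "New-onset PCS values are defined as values that were not PCS at baseline and were PCS post-baseline".

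On values outside the measurable range, the nearest rule is in Appendix A4: "All values below or above a limit of detection (e.g. <0.1 or >100) will be listed as such". It concerns listings and does not say how such a value is classified in a table. Under SAP 5.1.2, percentages use the non-missing observations; under 5.1, missing vital signs are not replaced.

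**The concern.** A manual reading cannot determine a systolic pressure above the pressure to which the cuff was inflated. The protocol's limit therefore sets a ceiling on every compliant systolic value, and the SAP's absolute threshold lies above that ceiling. The thresholds appear not to have been checked against the measurement procedure.

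What is at stake is how a safety table will be read. The primary objective is safety, there is no comparator arm, and blood pressure is measured at every follow-up visit. A systolic High column full of zeros looks like reassurance, although the procedure could produce nothing else. The by-visit means and changes are cut off from above as well, and nothing in the planned output would tell the reader so.

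**Working it through.** The plan has no figure of its own to reproduce. On sample size it says "No formal sample size calculations have been performed", and it gives no blood pressure distribution. The check is whether each criterion can be reached.

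**Inputs.** Ceiling 140 mmHg (Protocol 8.2.5). Shift-table bands below 86, 86 to 180, above 180 mmHg (SAP 5.8.6). PCS High above 180 mmHg or a rise of at least 25 mmHg (SAP Appendix A2). Maximum enrolment 87 (Protocol 9.2).

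**Step 1: absolute threshold.** 180 − 140 = 40 mmHg. No value at or below 140 exceeds 180, so the shift-table High cell and the absolute part of PCS High are both empty for compliant readings.

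**Step 2: rise criterion.** It needs baseline + 25 ≤ 140, so baseline ≤ 140 − 25 = 115 mmHg.

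| Baseline (mmHg) | Value needed (mmHg) | Measurable under the limit? |
|---|---|---|
| 110 | 135 | yes |
| 115 | 140 | yes, at the limit |
| 120 | 145 | no |
| 130 | 155 | no |
| 140 | 165 | no |

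**Step 3: other criteria.** The problem is confined to high systolic pressure. From a baseline of 130 mmHg, a 25 mmHg fall to 105 can be measured and is flagged PCS Low, while a 25 mmHg rise to 155 cannot be measured. Diastolic High (above 110 mmHg) lies below 140, and the 20 mmHg diastolic rise is reachable from any baseline up to 140 − 20 = 120 mmHg.

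**Step 4: what happens to a reading not determined at 140.**

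| How the site records it | Shift table | PCS High |
|---|---|---|
| 140 | Normal (86 ≤ 140 ≤ 180) | only if baseline ≤ 115 |
| blank | drops out of the percentages | not evaluable |
| above 140, as text | no rule; listed only | no rule |

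Neither document says which entry is to be made.

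**Step 5: how many could be affected.** The documents do not say. As an illustration only, assume systolic pressure is normally distributed with mean 105 to 125 and SD 10 to 15 mmHg:

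- The share with baseline ≤ 115 runs from Φ((115 − 125)/10) = Φ(−1) = 16% to Φ((115 − 105)/10) = Φ(1) = 84%.
- The expected number with a true value above 140 at one reading runs from about 0 (mean 105, SD 10) to 87 × (1 − Φ((140 − 125)/15)) = 87 × 0.159 = 13.8, about 14 of 87.

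**The case against.** The strongest reply has five parts.

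- **PCS High is not dead.** A reader might infer that the new-onset PCS table must also show no high systolic values. The documents do not support that. The rise criterion is an alternative, and a participant who goes from 110 to 135 mmHg is flagged. Only the shift-table column and the absolute part of PCS High are empty by construction.
- **Capped readings are not necessarily counted as normal.** A reader might infer that they always are. That holds only in the shift table and only if the site enters 140. Even then, the reading is PCS High when baseline was 115 mmHg or below. Appendix A4 also keeps out-of-range values visible in the listings if they are recorded as such.
- **The ceiling is not absolute.** The protocol says should, so some readings above 140 mmHg may exist. Inclusion values may be carried over from the parent study, whose cuff rule is not in these documents.
- **The tables are minor.** Vital signs come under other analyses in Protocol 9.4.4, not under the primary or secondary endpoints. Raised blood pressure is not among the risks in Protocol Table 2, uncontrolled cardiovascular disease is excluded, and Protocol 8.9 sends clinically significant abnormal findings after inclusion to adverse event reporting.
- **It is late.** SAP version 1.0 is dated 24 January 2024, in a study running from November 2021 to November 2024. A new recording code cannot by itself recover how earlier readings were entered.

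All five stand as limits on the size of the problem. None supplies a classification rule for capped readings or makes the High column informative.

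**Conclusion.** The mismatch is real. For readings taken as the protocol directs, the systolic High column of the shift table is zero whatever the true pressures, because its threshold is 40 mmHg above the ceiling. PCS High rests on the rise criterion alone and cannot be met from a baseline above 115 mmHg. The handling of capped readings is undefined.

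This rests on compliance with the 140 mmHg limit and on the fact that a cuff cannot show a systolic pressure above its own inflation. The number of participants affected is unknown; the range of 0 to about 14 of 87 depends wholly on assumed distributions. The primary endpoint analysis is untouched. The point is worth correcting because the correction is cheap and the uncorrected table invites false reassurance.

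A reader might also infer that any new value above 140 mmHg should count as PCS High. The documents give no basis for that. It would flag a move from 138 to 142 mmHg, which meets neither part of the Appendix A2 rule. Whether any threshold should change is for the sponsor.

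**What to change.** Reconcile Protocol 8.2.5 with SAP 5.8.6 and Appendix A2. The proposal here does not touch the cuff rule. In the SAP:

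1. Where the record allows it, tabulate a systolic pressure not determined at the inflation limit as its own category, above measurable range, in the shift table and the by-visit summaries. Do not enter it as 140 and Normal, or as missing. Give sites a matching recording instruction.
2. Footnote the vital-signs tables: systolic values above 180 mmHg are not observable under Protocol 8.2.5, so a zero in that column is not evidence of no high values.
3. Report the systolic rise criterion with the number of participants with baseline at or below 115 mmHg as its evaluable denominator.

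Membership of the new category should not in itself count as PCS High. The existing rise rule continues to apply where baseline permits: a value above 140 from a baseline of 115 or below is a rise of more than 25 mmHg.

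The cost is one table row, one footnote and one recording instruction. Capped readings already entered as 140 or left blank may not be recoverable; if so, the footnote should say that.
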